We performed a long-term study to assess the safety and potential of BCI-FES therapy. Nine chronic stroke subjects (>6 months post-ictus) with gait impairment due to foot-drop underwent 12 sessions of BCI-FES therapy (3 sessions/week, for 4 weeks). The primary outcome measure was gait velocity. Secondary outcomes were dorsiflexion active range of motion (AROM), leg motor Fugl-Meyer score, gait endurance (6-min walk test), and fall frequency. These outcomes were assessed before, on a weekly basis, and 1 month after completion of the BCI-FES therapy (Fig. 3). No subjects experienced a significant decrement in any outcome measure and there were no adverse events, indicating that BCI-FES therapy is safe. In post-hoc analysis, 6 out of 9 (66.7%) subjects had a significant improvement in gait velocity at 1 month post-therapy (average increase of 51%, or  $0.21 \pm 0.15$  m/s). While no spatial cortical reorganization was observed in any subject at the end of therapy, the Cz channel (electrode over the foot motor area) exhibited an increase in alpha- and beta-band event-related desynchronization/synchronization (ERD/ERS) magnitude in 5 of these 6 (83.3%) subjects. Conversely, these EEG changes did not occur in the 3 subjects with no gait velocity improvement. This suggests the existence of a neural process underlying gait velocity improvements. Subjects with low gait velocity (<0.4 m/s) and poor dorsiflexion AROM (<5 degrees) at baseline were 150% more likely than those with moderate-to-high gait velocity (>0.4 m/s) or good-to-excellent AROM (>5 degree) to experience an increase in gait velocity. This highlights a potential promise of BCI-FES therapy in that it may be accessible and beneficial to stroke survivors whose baseline motor functions are too low for current or emerging interventions.

Describe the primary outcome variable(s), secondary outcome variables, and predictors and/or comparison groups as appropriate for the stated study objectives/specific aims:

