#### Eligibility Factors (Inclusion/Exclusion Criteria)

1. Click "Add Line" button above Eligibility Factors Table to add a inclusion/exclusion criteria
  - a. To change visibility of columns, click "Columns" button above Eligibility Factors Chart and select which Column rows to view.
2. Identify the factors for limited eligibility and provide a scientific rationale. Include additional rows for factors, as needed.

---

Category/Group Eligibility

Adults - all groups

Inclusion Criteria

1. Age 18-80 years inclusively at time of consent;
2. Radiologically confirmed stroke, ischemic or intracerebral hemorrhage (ICH) in etiology, with day of onset at least 26 weeks prior to day of randomization
3. Gait velocity < 0.8 m/s at screening and baseline visits.
4. Foot-drop in affected limb as defined by dorsiflexion active range of motion (AROM) via goniometry in seated position foot dangling is less than passive range of motion and less than 15 degrees.
5. Plantarflexors spasticity < 3 on modified Ashworth Scale;
6. Can walk > 10 m (with or without ankle foot orthosis (AFO), and cane or walker permitted) at a supervised level;
7. Can tolerate FES with pain no more than 4 on pain analog scale and has adequate muscle response of dorsiflexion  $\geq$  10 degrees;
8. Passive Range of Motion at least 0 degrees ankle dorsiflexion in subtalar neutral or with FES

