Aim 1: The primary outcome measure will be gait velocity, which is directly linked to disability and social re-integration after stroke. Gait velocity will be assessed by measuring the time to traverse the middle 6 m of a 10-m walkway (5 repetitions/assessment). Secondary outcomes include: 1. Gait endurance: The distance walked over 6 minutes. 2. Fall Frequency: Number of falls experienced weekly. 3. Leg Motor Fugl-Meyer (FM) Score: Assessed according to the FM rating system. 4. Dorsiflexion Active Range of Motion (AROM) and torque: The paretic foot will be placed in an articulated brace which maintains the ankle at neutral during idling, while fixing the tibia perpendicular to the ground and the femur horizontal to the ground. The brace will be instrumented with an electro-goniometer and torque meter to automatically measure the maximum dorsiflexion AROM and torque (over 3 trials). 5. EEG Map: Subjects will undergo 64-channel EEG recording as they engage in 100 alternating 10-s long epochs of idling and attempted dorsiflexion. The EEG ERD/ERS, defined as the drop/rise in alpha (8-12 Hz) and beta (13-30 Hz) band power during attempted dorsiflexion (compared to idling), will be calculated and averaged over all epochs and across all channels. A pre-intervention baseline for each outcome will first be established. Subsequently, measurements will be performed at 1 week intervals during the intervention phase (total of 3), immediately after the intervention phase, as well as 1 and 3 months after completion of interventions. The primary efficacy outcome and endpoint will be gait velocity immediately after the intervention phase. Aim 2 (subgroup analysis of Phase II clinical trial) Since stroke is a heterogeneous disease, responsiveness to rehabilitation therapy is not uniform across all subpopulations. Hence, it is important to ensure that any new therapy, e.g. BCI-FES therapy, is matched to subpopulations that will benefit the most. The following set of baseline characteristics will be assessed during the pre-intervention phase (Fig. 6, Phase 2) for Groups 1 and 2 to determine which features influence responsiveness to BCI-FES therapy: 1. Baseline gait velocity, dorsiflexion AROM and torque: Baseline gait velocity and dorsiflexion AROM and torque will be taken from Aim 1. 2. TA volitional electromyogram (EMG): TA EMG will be assessed by having subjects attempt dorsiflexion while seated with tibia perpendicular to ground. EMG will be acquired by a bioamplifier with surface electrodes placed over the TA muscle. Subjects will be categorized as either

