#### **Statistical Considerations**

Is a statistical analysis plan appropriate for this qualitative study design?

Yes

Describe the statistical methods for the stated specific aims and hypotheses. Your analysis plans should match the stated study specific aims and hypotheses:

Aim 1: The study design is a parallel randomized controlled trial with two arms: BCI-FES dorsiflexion therapy and dose-matched conventional physical therapy. A total of 80 subjects (which includes 10% attrition) will be randomized with 1:1 ratio into the two study arms. The primary outcome is gait velocity and the secondary outcomes are gait endurance, fall frequency, leg motor FM score, and dorsiflexion AROM and torque. Outcomes measures will be evaluated at baseline, weekly during therapy, immediately post-intervention, and 1- month and 3-months post-therapy. The primary efficacy analysis (with intent-to-treat analysis with respect to treatment randomized) will be based on a linear mixed model (LMM) with gait velocity measured at baseline weeks 1-4 (time 0, 1, 2, 3, and 4) with time, treatment group and group by time interaction assess the difference in the rates of change (improvement) in gait velocity between treatment groups. Model estimation will be based on restricted maximum likelihood (REML) with unstructured covariance among repeated measurements over time. The LMM will also be applied to evaluate group difference for secondary outcomes and secondary endpoints at 1- and 3-months post-therapy. In order to determine if  $\mu$  and  $\beta$  ERD/ERS significantly changes over the 4 weeks of therapy, the ERD and ERS magnitude will be calculated for each EEG channel across all attempted dorsiflexion epochs, and for each assessment. The Mann-Whitney U test will be used to determine if any significant changes in the magnitude of ERD/ERS at each assessment with respect to the baseline. Based on the findings, each subject will be categorized as demonstrating significant changes in ERD/ERS or not. Next, all subjects will also be categorized on whether they experienced a detectable increase in gait velocity (defined as an increase in gait velocity of  $>0.16$  m/s with respect to baseline). A Chi-square test will be used to assess if there is a difference between the proportion of those with changes in ERD/ERS magnitude in those who had gait improvement within the BCI- FES therapy group. This will also be repeated for the control group. In addition, to determine if the presence of significant ERD/ERS changes was affected by group, the Chi-square test will be repeated by using BCI-FES group as the observation and the control group as the expected values. Aim 2: Data from Aim 1 will be used for analysis in this aim. The primary outcome is gait velocity immediately post-BCI-FES therapy, and the secondary outcomes are the same as in Aim 1. To test whether specific stroke features (e.g. baseline gait velocity, dorsiflexion AROM, etc.) modify response to treatment over

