**Power Analysis:** For Aims 1 and 2, the power analysis was based on a LMM with two treatment groups and 5 repeated measures (baseline and after weeks 1-4) with a significance level of 0.05. Previous studies have examined the clinically meaningful gait improvement (minimal clinically important difference) of 0.16 m/s, including a multicenter randomized clinical trial that includes conventional physical therapy. Thus, to ensure clinically meaningful effect size, we assume conventional therapy will have an improvement of 0.25 m/s after 4 weeks of treatment. Data from prior studies as well as our own preliminary data (n=9) found that the between-subject variance in gait velocity of about 0.16 m/s and the within-subject correlation of about 0.95. Table 1 below shows the power to detect improvement of BCI-FES over conventional therapy of 30% - 40%. Thus, for the proposed study with n=80 patients (40 per arm) has 92% to 94% power to detect an effect size/improvement of 35% for various between-subject variance (0.15 m/s to 0.17 m/s) in determining treatment efficacy (Aim 1). We note that n=80 total has been intentionally inflated in order to accommodate the objectives of aim 2 to examine modifying factors, such as TA MEP (primary modifying factor), on treatment. That is, for n=30 per arm the power to determine efficacy (aim 1) is 85% for detecting an effect size/improvement of 35% (between-subject variance 0.16 m/s); thus, increasing to n=40 allows for detecting modifying factor on treatment (aim 2) when the interaction effect smaller (effect size 28% can be detected with 79% power). Table 1: Power to detect improvement in gait velocity due to BCI-FES over conventional therapy for n=80 with various between-subject variance (aim 1). Between-Subject Variance Effect Size (Improvement) 0.15 0.16 0.17 30% 87.3% 85.2 % 83.0% 35% 94.5% 93.5% 92.1% 40% 98.3% 97.7% 97.0% Aim 3: Total sample size of n=20 will have 82% power to detect an R-square of 0.16 (attributed to the effect of interest, e.g., w x group) adjusted for baseline measurement and main effects whose total contribution R-square is 0.5 (for 3 independent variables) in a multiple regression model.

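### The Aim 1 primary model omits baseline dorsiflexion AROM by time; adding it before unblinding is a cheap option whose power gain rests on an assumed correlation

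*Combined protocol and SAP*

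**What the plan says.** Under Statistical Considerations, the Aim 1 primary efficacy analysis is an intention-to-treat linear mixed model of gait velocity at times 0 to 4, "with time, treatment group and group by time interaction assess the difference in the rates of change (improvement) in gait velocity between treatment groups". It is fitted by REML with an unstructured covariance. No baseline covariate is listed.

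AROM appears in four other places.

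- **Eligibility Factors, inclusion item 4.** Foot-drop is defined by "dorsiflexion active range of motion (AROM) via goniometry in seated position foot dangling is less than passive range of motion", with an upper limit of 15 degrees. Every subject therefore has a screening value.
- **Study Design, endpoints.** AROM is a secondary outcome, measured by electro-goniometer in an articulated brace, with a baseline taken before the intervention. For Aim 2, "Baseline gait velocity and dorsiflexion AROM and torque will be taken from Aim 1".
- **Background & Purpose.** The pilot report says "Subjects with low gait velocity (<0.4 m/s) and poor dorsiflexion AROM (<5 degrees) at baseline were 150% more likely" than the remaining subjects to gain walking speed. The Aim 2 hypothesis lists AROM among the baseline features expected to influence the response to BCI-FES.
- **Statistical Considerations, Aim 2.** AROM is named as a possible modifier in a group by time by factor model.

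**The concern.** The primary test compares rates of change. If a value recorded before treatment explains part of the variation in those rates, leaving it out keeps that variation in the error of the slope contrast. The plan itself singles out AROM as related to gait response, yet uses it only in Aim 2.

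Precision is also scarcer than planned. The renewal form (UCI Progress) reports 62 subjects randomised in Aim 1, against the 80 on which the power table rests.

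A main effect of AROM would not help, because a subject's overall level already cancels out of a slope. Only AROM by time can reduce the error.

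**Working it through.** **1. Reproduce the plan's power.** The inputs are in the power analysis under Statistical Considerations: "5 repeated measures (baseline and after weeks 1-4) with a significance level of 0.05"; "we assume conventional therapy will have an improvement of 0.25 m/s after 4 weeks of treatment"; prior data that "found that the between-subject variance in gait velocity of about 0.16 m/s and the within-subject correlation of about 0.95"; 40 per arm; effects of 30% to 40% of the control improvement. The value 0.16 reproduces the table only as a variance, and only with a two-sided test.

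- Times 0 to 4 have a sum of squares about their mean of 4 + 1 + 0 + 1 + 4 = 10.
- Slope variance per subject = 0.16 × (1 − 0.95) / 10 = 0.0008.
- Standard error of the slope difference = √(2 × 0.0008 / 40) = 0.006325.
- Slope difference for a 30% effect = 0.30 × 0.25 / 4 = 0.01875 m/s per week.
- z = 0.01875 / 0.006325 = 2.965; power = Φ(2.965 − 1.960) = 84.2%, against 85.2% stated.

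All nine cells of Table 1 reproduce within 1 point. At 35% and variance 0.16 the result is 93.3% (stated 93.5%). The two further figures also agree: 30 per arm at 35% gives 85.0% (stated 85%), and a 28% effect at 40 per arm gives 79.0% (stated 79%).

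**2. Add AROM by time, with a link in both arms.** Let r be the within-arm correlation of baseline AROM with the individual slope. The slope variance is multiplied by (1 − r²). At r = 0.5 it is 0.0008 × 0.75 = 0.0006, the standard error is 0.005477, z = 3.423 and power is 92.8%. A simulation of the slope regression (20,000 runs) gave 83.6% without and 92.2% with the covariate.

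**3. Link under BCI-FES only.** A common AROM by time coefficient then averages r and 0, giving r/2. Residual variance is 1 − r² + r²/4 in the BCI-FES arm and 1 + r²/4 in the control arm, with mean 1 − r²/4. At r = 0.5 the reduction is 6.25%.

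**4. Results.** Gains are in percentage points, variance 0.16. The last column takes the 62 randomised as 31 per arm; equal arms are an assumption.

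| r | 30% effect, 40/arm, both arms | 30% effect, 40/arm, BCI-FES only | 35% effect, 40/arm, both arms | 30% effect, 31/arm, both arms |
|---|---|---|---|---|
| Unadjusted power | 84.2% | 84.2% | 93.3% | 74.2% |
| 0.2 | +1.4 | +0.4 | +0.9 | +1.7 |
| 0.3 | +3.2 | +0.8 | +1.9 | +3.9 |
| 0.4 | +5.6 | +1.4 | +3.2 | +7.1 |
| 0.5 | +8.6 | +2.2 | +4.6 | +11.2 |

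**5. The nil case.** The 0.0008 that reproduces Table 1 is entirely within-subject residual, so within an arm all subjects share one true slope. In that model no baseline covariate can predict slope. The gain is zero and about one degree of freedom is lost. Any positive r assumes real differences between subjects' slopes.

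**6. What the pilot can say about r.** Six of nine subjects improved. If 150% more likely means a risk ratio of 2.5, only two splits fit: 5/6 against 1/3 (phi 0.50, Fisher p = 0.23) and 4/4 against 2/5 (phi 0.63, p = 0.17). Read as an odds ratio of 2.5, a split of 5/7 against 1/2 fits, with phi = (5×1 − 2×1)/√(7×2×6×3) = 0.19. The same sentence is therefore compatible with values from about 0.2 to above 0.6, and none of them is a correlation of AROM alone with slope.

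**The case against.** The strongest reply is that the plan is valid as written and that nothing in it establishes AROM as prognostic. Most of this stands.

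- The pilot had no control arm, and the Aim 2 hypothesis concerns response to BCI-FES. That is effect modification, for which the gain is about 0.4 to 2.2 points at 40 per arm. Nothing says that AROM predicts gain under conventional therapy.
- The pilot statement combines poor AROM with low gait velocity, so AROM's own contribution is not identified. It is post hoc with n = 9, and response was judged 1 month after therapy, whereas the primary contrast ends at week 4.
- Eligibility caps AROM below 15 degrees, which may weaken any correlation.
- Enrolment and treatment are over and the DSMB has seen interim data, so this is a late change to a primary model.

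A reader might infer that the pilot fixes the gain at up to about 9 points. It does not. That figure needs r of about 0.5 in both arms, an input the documents do not supply. Nor is it a ceiling: r = 0.6 would give 11.7 points at 40 per arm.

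Two parts of the reply are weaker. The nil case sits badly with Aim 2, which presupposes that slopes vary with baseline features, and the primary model's unstructured covariance does not force a common slope. The Aim 2 model does not serve the same purpose either: it tests whether AROM modifies the treatment effect and leaves the precision of the Aim 1 contrast unchanged.

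**Conclusion.** The omission is real, and adding AROM by time is a reasonable optional improvement. It is not the correction of an error: under randomisation the unadjusted slope contrast is valid, and a reader who takes the omission for bias would go beyond the documents.

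The one-arm link is all that the documents support, and it is worth little. The larger both-arm gains need a prognostic link in the control arm and true slope heterogeneity, neither of which is documented. At the 35% effect on which the plan's power claim rests, even r = 0.5 in both arms adds only 4.6 points at 40 per arm. The case is somewhat stronger at the number actually randomised, where unadjusted power for a 30% effect is about 74% and the both-arm gain is about 1.7 to 11 points for r = 0.2 to 0.5.

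**What to change.** In the Aim 1 paragraph of Statistical Considerations, by an amendment dated before unblinding:

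- Name one AROM measure, either the screening goniometry of inclusion item 4 or the braced electro-goniometer baseline. The two are taken differently and should not be mixed. Use only values obtained before treatment starts.
- Add that measure, continuous and mean-centred, and its interaction with time to the gait-velocity model.
- Keep group by time as the primary contrast.
- Report the model without AROM as a sensitivity analysis.
- Leave the Aim 2 three-way model unchanged.

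The measurements are already part of the study, so no new data are needed. The cost is two fixed effects, about one degree of freedom on the slope contrast, and the need to document a late change. It still appeared feasible at this renewal: one Aim 1 subject awaited final assessment, data analysis lay ahead, and the Data Safety Monitoring Plan keeps the investigative team blinded to the outcome data.

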
treatment duration, a LMM model with three-way interaction (group, time, modifying factor) will be used to test whether the slope of the three-factor interaction is zero (specific stroke feature does not modify response to treatment). Aim 3: The aim is designed as a randomized controlled study with two arms: BCI-FES dorsiflexion therapy and BCI-robotic orthosis therapy. A total of 20 subjects will be recruited and randomized with 1:1 ratio into the two arms. The primary outcome is gait velocity, and the secondary outcomes are ankle torque and active range of motion. The main interest is to evaluate if the correlation between  $M1 \rightarrow \text{EMG}$ ,  $w$ , (normalized range: 0-1), and gait velocity is different between the two study groups averaged over time after treatment, adjusted for baseline outcome measure. For example, with outcome gait velocity, the analysis will be based on a regression model with group,  $w$ , and their interaction, adjusted for baseline gait velocity. The relationship between both  $w$  with secondary outcomes will be similarly analyzed.

Describe the statistical method(s) that will be used to analyze the primary outcome(s) or endpoints:

The primary statistical methods for primary outcome, gait velocity, is already described in Aim 1 above.

If appropriate describe secondary or post hoc analyses of primary outcome(s) or other exploratory analysis and if necessary, provide a breakdown of the methods used per outcome or endpoint:

The statistical method for secondary outcome measures is similar to the primary outcome, and is already described in Aim 1 and 2 above.

**Sample Size Determination:** Explain how the overall target sample size was determined (e.g., power analysis; precision estimation), providing justification of the effect size for the primary outcome based on preliminary data, current knowledge/literature and/or cost consideration; if appropriate, provide sample size justification for secondary outcomes. Power analysis should (at least) match the primary outcome/endpoint:

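### The Aim 1 mixed model lists no baseline adjustment and leaves the 1- and 3-month group difference undefined; a common baseline mean for both arms would settle both points at no cost in patients

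*Combined protocol and SAP*

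**What the plan says.** Under Statistical Considerations, the Aim 1 primary model takes "gait velocity measured at baseline weeks 1-4 (time 0, 1, 2, 3, and 4"), so baseline is itself one of the responses. Its terms are given as "with time, treatment group and group by time interaction assess the difference in the rates of change (improvement) in gait velocity between treatment groups". Estimation is by "restricted maximum likelihood (REML) with unstructured covariance among repeated measurements over time". Nothing equates the arms at time 0, and no baseline covariate is listed for Aim 1.

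For everything beyond the primary slope the text is: "The LMM will also be applied to evaluate group difference for secondary outcomes and secondary endpoints at 1- and 3-months post-therapy". A later answer in the same section adds: "The statistical method for secondary outcome measures is similar to the primary outcome". Neither sentence says whether the difference at a follow-up visit is between the arms' means at that visit or between their changes from baseline.

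Aim 3 is written differently: "the analysis will be based on a regression model with group", the coherence measure and their interaction, with explicit adjustment for baseline gait velocity. The endpoint definitions under Study Design describe the Aim 1 primary endpoint as gait velocity just after the intervention phase, which is a level and not a change.

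**The concern.** Randomisation makes the expected baseline means of the two arms equal. A model that estimates them separately does not use that fact. How much this costs depends on the contrast taken from the model.

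- The group-by-time contrast subtracts the whole observed baseline difference. It is valid and nearly efficient when the correlation is high, but it over-corrects slightly.
- The difference in visit means subtracts none of it, so the full between-patient spread stays in the standard error.

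Because the follow-up contrast is unnamed, an analyst could report either and still claim to follow the plan. The Aim 1 hypothesis is that gains are longer-lasting as well as greater, so the 1- and 3-month comparisons bear on a stated hypothesis.

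**Working it through.** **Inputs.** The sample size text gives "between-subject variance in gait velocity of about 0.16 m/s and the within-subject correlation of about 0.95" and "two treatment groups and 5 repeated measures (baseline and after weeks 1-4) with a significance level of 0.05". It also gives 40 per arm, a control improvement of 0.25 m/s over 4 weeks, and an effect of 35%, that is 0.35 × 0.25 = 0.0875 m/s at week 4, or 0.021875 m/s per week. The test is taken as two-sided, since the plan does not state sidedness.

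**The plan's own figure first.** With t = 0 to 4, the sum of squares about the mean is 10. The slope SD is sqrt(0.16 × 0.05 / 10) = 0.0283. The standard error of the slope difference is 0.0283 × sqrt(2/40) = 0.00632. The ratio is 0.021875 / 0.00632 = 3.46, so power is 93.3%, against 93.5% in Table 1. All nine cells of the table reproduce within one point. This also shows that 0.16 acts as a variance (SD 0.40 m/s): read as an SD, it gives power of essentially 100% in every cell.

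**One follow-up visit.** With variance V at both times, correlation r between baseline and the visit, n per arm, and a separate mean at each visit, the standard errors of the arm difference are:

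- visit means, baselines free: sqrt(2V/n)
- group by time (change from baseline): sqrt(4V(1 − r)/n)
- baseline-adjusted (common baseline mean or covariate): sqrt(2V(1 − r²)/n)

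The variance saved by adjustment relative to change is 1 − (1 + r)/2 = (1 − r)/2. With V = 0.16 and n = 40:

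| r | Visit means | Change | Adjusted | Visit means / adjusted | Change / adjusted | Variance saved against change |
|---|---|---|---|---|---|---|
| 0.95 (plan) | 0.0894 | 0.0283 | 0.0279 | 3.20 | 1.013 | 2.5% |
| 0.90 (assumed) | 0.0894 | 0.0400 | 0.0390 | 2.29 | 1.026 | 5% |
| 0.80 (assumed) | 0.0894 | 0.0566 | 0.0537 | 1.67 | 1.054 | 10% |
| 0.70 (assumed) | 0.0894 | 0.0693 | 0.0639 | 1.40 | 1.085 | 15% |
| 0.50 (assumed) | 0.0894 | 0.0894 | 0.0775 | 1.15 | 1.155 | 25% |

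At an assumed 0.84 the saving is 8%. The standard-error ratios and percentage savings do not depend on V or n, so the last three columns carry over to any continuous outcome with that correlation. A generalised least squares calculation over all seven visits, with constant correlation 0.95, gives the same 3.20 and 1.013 at 1 and 3 months.

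**Power for 0.0875 m/s at one visit, r = 0.95.** 16% for visit means, 87% for change and 88% adjusted. The renewal form reports 62 randomised in Aim 1. With an even split assumed (31 per arm), the figures are 14%, 78% and 79%.

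**Primary slope.** With a common baseline, the information on the slope difference rises from 10 to 30 − 100r/(1 + 4r), in the same units. At r = 0.95 that is 10.21, a variance ratio of 0.980, so about 2% is saved.

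**Chance imbalance.** One standard error of baseline difference is 0.0894 m/s, about the size of the target effect. Visit means carry r times the imbalance in expectation, or 0.95 × 0.0894 = 0.085 m/s. The change contrast is off by (1 − r) times it, or 0.05 × 0.0894 = 0.0045 m/s, in the opposite direction.

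**The case against.** The strongest reply is that the only treatment contrast the plan names is group by time. The follow-up sentence applies the same model, and the later answer ties the secondary method to the primary one. On that reading the baseline difference has already been removed, and the loss for gait velocity is 1.3% in standard error and under one point of power. The model as written is valid and unbiased in a randomised trial. This stands, and it is why the point is an improvement and not an error.

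It does not settle the matter. A slope over weeks 0 to 4 does not define a contrast at 1 or 3 months, and the endpoint definition is worded as a level.

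Three stronger inferences are tempting, and the documents do not support them.

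- A reader might conclude that free baseline means by themselves make the follow-up differences unadjusted, with three times the necessary standard error. They do not: that requires the visit-mean reading and a correlation of 0.95 at 1 and 3 months. The plan gives 0.95 for gait velocity in its baseline-to-week-4 power model only, and no correlation for any other outcome.
- A reader might say that the change contrast fails to correct chance imbalance. It removes the observed difference and slightly over-corrects.
- A reader might bring in the absence of a described stratification, together with the pilot's link between baseline speed and response. That link is a post-hoc finding in nine patients about who responds to BCI-FES. It concerns effect modification, which Aim 2 tests through a three-way interaction and which a common baseline mean would not address.

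**Conclusion.** The point holds as a free improvement together with a definition that is missing. On the reading the text favours, baseline adjustment saves about 2.5% of variance for gait velocity. For other continuous outcomes it saves 8% to 25% if their correlations are between 0.84 and 0.50, a range that is assumed and not documented. The 3.2-fold standard error, and power of 16% against 88%, is the upper end of what the undefined wording permits and not what the plan prescribes.

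The figures rest on equal variance at baseline and follow-up, complete data, a separate mean at each visit, and an effect of 0.0875 m/s persisting to the follow-up visit. They do not apply to fall frequency, which is a weekly count. The primary slope test and its stated power are not called into question.

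**What to change.** In the Aim 1 models for gait velocity and the continuous secondary outcomes (gait endurance, Fugl-Meyer score, dorsiflexion range of motion and torque), do one of two things: drop the group effect at time 0 and keep group by time afterwards, so that both arms share one baseline mean (a constrained longitudinal model); or move baseline to the covariate side. Then state that the reported quantity is the baseline-adjusted group difference at end of therapy, at 1 month and at 3 months. Fall frequency needs its own statement suited to a count.

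This takes a line of analysis-plan text and one model term, with no new data or patients. The renewal form records that treatment is complete, that interim data have gone to the DSMB and that analysis is still to come. The change should therefore be dated and justified before any unblinded comparison, with the planned unconstrained primary model reported alongside.
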